7.7 Tolerability Assessment

The number and percentage of subjects reporting burning or tasting irritation (Grade 1 or higher) will be tabulated by severity.

7.8 Safety Assessment

7.8.1 Safety Reporting

7.8.1.1 Definitions

Adverse event - An adverse event (AE) means any untoward medical occurrence associated with the use of a drug in humans, whether or not considered drug related. An AE (also referred to as an adverse experience) can be any unfavorable and unintended sign (e.g., and abnormal laboratory finding), symptom, or disease temporally associated with the use of the drug, without judgment about causality. An adverse event can arise from any use of the drug (e.g., off-label use, use in combination with another drug) and from any route of

administration, formulation, or dose, including an overdose.

Adverse reaction - An adverse reaction means any adverse event caused by a drug. Adverse reactions are a subset of all suspected adverse reactions for which there is reason to conclude that the drug caused the event.

Suspected adverse reaction - Suspected adverse reaction means any adverse event for which there is a reasonable possibility that the drug caused the adverse event. For the purposes of safety reporting, "reasonable possibility" means there is evidence to suggest a causal relationship between the drug and the adverse event. Suspected adverse reaction implies a lesser degree of certainty about causality than adverse reaction, which means any adverse event caused by a drug.

Suspected adverse reactions are the subset of all adverse events for which there is a reasonable possibility that the drug caused the event. Inherent in this definition (of suspected adverse reaction), and in the requirement to report them is the need for the sponsor to evaluate the available evidence and make a judgment about the likelihood that the drug actually caused the adverse event.

Unexpected Adverse Event - An adverse event or suspected adverse reaction is considered "unexpected" if it is not listed in the literature for East Indian sandalwood oil.

Serious - An adverse event or suspected adverse reaction is considered "serious" if, in the view of either the investigator or sponsor, it results in any of the outcomes listed in Section 6.4.

Life-threatening - An adverse event or suspected adverse reaction is considered "life-threatening" if, in the view of either the investigator or sponsor, its occurrence places the patient or subject at immediate risk of death. It does not include an adverse event or suspected adverse reaction that, had it occurred in a more severe form, might have caused death.

If either the sponsor or investigator believes that the event meets the definition of life-threatening, it must be considered life-threatening.

7.8.1.2 Adverse Events

Information about all AEs, whether volunteered by the subject, discovered by investigator questioning, or detected through physical examination, or other means, will be collected and recorded on the Adverse Events page of the CRF and followed as appropriate. Adverse events will be coded using an internationally recognized dictionary (see Section 7.8.1).

Medical conditions/diseases present before starting study treatment are only considered adverse events if they worsen after starting study treatment (ie, any procedures specified in the protocol). Adverse events occurring before starting study treatment, but after signing the informed consent form, are recorded on the Medical History/Current Medical Conditions page of the CRF.

As far as possible, each AE will also be described by:

- its duration (start and end dates),
- the severity grade (mild, moderate, severe),
- its relationship to the study product (definite, probably, possibly, unlikely, or not related),
- the action(s) taken, and,
- the outcome, as relevant.

Severity of adverse events

The investigator is to classify the severity of an AE according to the CTCAE 4.0 definitions.

Relationship of adverse event to study treatment

The investigator is to classify the relationship of the AE to the investigational product according to the definitions outlined in Table 7-8.

Table 7-8 Terms for Defining Relationship of Adverse Event to Study Product

Association	Definition
Not related	(1) the existence of a clear alternative explanation (eg, mechanical bleeding at surgical site) or (2) non-plausibility, eg, the subject is struck by an automobile or develops cancer a few days after product administration.
Unlikely related	A clinical event, including laboratory test abnormality (if applicable), with an improbable time sequence to product administration and in which other drugs, chemicals for underlying disease provide plausible explanations.
Possibly related	A clinical event, including laboratory test abnormality (if applicable), with a reasonable time sequence to administration of the drug, but which could also be explained by concurrent disease or other drugs or chemicals.
Probably related	A clinical event, including laboratory test abnormality (if applicable), with a reasonable time sequence to administration of the drug, unlikely to be attributed to concurrent disease or other drugs or chemicals, and which follows a clinically reasonable response on withdrawal.
Definitely related	A clinical event, including laboratory test abnormality (if applicable), with an established temporal or other association (eg, re-challenge) and the event is not reasonably explained by the subject's known clinical state or any other factor, based on available information.

7.8.1.3 Serious Adverse Events

An AE can be severe, but not necessarily serious. A serious adverse event (SAE) or suspected adverse reaction as 'serious' if, in the view of either the investigator or sponsor, results in any of the following outcomes:

- death;
- a life-threatening adverse events
- inpatient hospitalization or prolongation of existing hospitalization;
- a persistent or significant incapacity or substantial disruption of the ability to conduct normal life functions;
- a congenital anomaly or a birth defect.

Important medical events that may not result in death, be life-threatening, or require hospitalization may be considered serious when, based upon appropriate medical judgment, they may jeopardize the subject and may require medical or surgical intervention to prevent one of the outcomes listed above.

Events not considered to be serious AEs are hospitalizations for the:

- █ routine treatment or monitoring of the studied indication, not associated with any deterioration in condition;
- █ treatment, which was elective or pre-planned, for a pre-existing condition that did not worsen; and/or
- █ treatment on an emergency, outpatient basis for an event not fulfilling any of the definitions of serious given above and not resulting in hospital admission.

If either the sponsor or investigator believes that the event is serious, the event must be considered serious and evaluated by the sponsor.

Information about all SAEs will be collected and recorded on the Serious Adverse Event Report Form and reported to the Medical Monitor:

[name]., Ph.D.
Dept. Of Radiation Oncology
[name]
[name]
[contact]
Email: [contact]

To ensure subject safety each SAE must also be reported to the sponsor within 24 hours of learning of its occurrence and, if applicable, to the responsible Institutional Review Board (IRB) according to their reporting requirements.

Pregnancy, although not itself an SAE, should also be reported on a Serious Adverse Event Report Form.

A death occurring during the study, or which comes to the attention of the investigator within 4 weeks after stopping treatment, must be reported.

Any serious adverse event occurring in a subject after providing informed consent and until 4 weeks after stopping study drug treatment must be reported

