Trial Design and Subject Population	
This trial will be a single-center, open-label, proof of concept trial to evaluate the efficacy, safety and tolerability of SAN005 treatment regimen when administered to adults at least 18 years of age for the prevention and treatment of oral mucositis.
 
Subjects will enter the Screening Period once the informed consent process has been completed. Subjects who are scheduled to receive radiation with or without concurrent chemotherapy and meet all of the inclusion criteria and none of the exclusion criteria will be eligible for the study:
 
Once subject eligibility is confirmed the subject will start SAN005 treatment on Day 1 of their radiation treatment. All subjects will receive active medication in the study with the first dose administered on Day 1.
 
Subjects will be instructed on the administration of study medication thrice daily throughout the duration of radiation therapy. Subjects will be evaluated by the physician once a week while receiving radiation therapy and then every other week once their radiation therapy has been completed, until their mucositis has resolved for the Final Study Visit.

Inclusion Criteria

Subjects will be included in the trial if they meet all of the following criteria:

1. Subjects with head and neck cancer involving the oropharynx or oral cavity, who are expected to undergo high dose radiation therapy (i.e., ≥ 60 Gy) that typically results in oral mucositis, with or without concurrent chemotherapy or biologic targeted therapy.
2. At least 18 years of age
3. Estimated survival of at least 6 months.
4. No prior radiation therapy to the head and neck area, and no chemotherapy within the last year except for induction chemotherapy delivered (or to be delivered) prior to the current course of radiation therapy
5. Female subjects of child-bearing potential must agree to use an adequate form of contraceptive (e.g., hormonal, barrier method or abstinence) prior to study entry and for the duration of the trial.
6. Are willing to refrain from using other treatments for oral mucositis until they consult with the study investigator(s).
7. Are able to give written informed consent in a manner approved by the Institutional Review Board and comply with the requirements of the study.

Exclusion Criteria

Subjects will be excluded from the trial if they meet any of the following criteria:

1. Have preexisting mucositis from other causes.

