- Request the subject to complete Day 1 of the diary and review for completeness and accuracy

Visit 3 to 8

Clinic visit with a radiation oncologist once a week till the end of treatment.

All study visits will have a \pm 2 day visit window during the radiotherapy.

- Query for adverse events
- Update concomitant medications and PEG tube usage
- Review the diary for the previous week
- Query for treatment regimen compliance
- Collect the study medication and weigh the study medication to determine usage
- Administer the QoL Questionnaire
- Administer the Numerical Rating Pain Scale (NRPS) as related to mouth pain and pain with swallowing. The NRPS will be recorded daily by the subjects between study visits
- Inspect the oral cavity and grade mucositis according to the RTOG Scale
- Record the subject's tolerability to the study drug
- Instruct the subject to return for the next study visit with study medication container and diary

Follow-up Period

Visit 9 to 10

Clinic visit with a radiation oncologist every other week after completion of radiotherapy until either mucositis resolves or it reaches Visit 10, whichever is earlier.

All study visits will have a \pm 2 day window during the follow-up period.

- Query for adverse events
- Update concomitant medications and PEG tube usage
- Review the diary for the previous week.
- Query for treatment regimen compliance
- Collect the study medication and weigh the study medication to determine usage
- Administer the QoL Questionnaire
- Administer the Numerical Rating Pain Scale (NRPS) as related to mouth pain and pain with swallowing. The NRPS will be recorded daily by the subjects between study visits.
- Inspect the oral cavity and grade mucositis according to the RTOG Scale
- Record the subject's tolerability to the study drug
- Instruct the subject to return for the next study visit with study medication container and diary

Trial Contacts

Name	Affiliation / Address	Responsibility
Santalis Corporation	[name] ☎ [contact] ✉ [contact]	Sponsor
[name].	Santalis Corporation [name] ☎ [contact] ✉ [contact] e-mail: [contact]	Sponsor Manager and contact for SAEs

Table of Contents

Contents

TITLE PAGE	1
Trial Contacts	6
Table of Contents.....	7
List of Tables.....	9
List of Figures	10
LIST OF ABBREVIATIONS AND DEFINITION OF TERMS	11
1 INTRODUCTION.....	12
1.1 Oral Mucositis	12
1.2 Santalis Oral Mucositis Treatment.....	12

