3. STUDY PLAN

3.1 Overall Study Design

This trial will be a single-center, open-label, proof of concept trial to evaluate the efficacy, safety and tolerability of SAN005 treatment regimen when administered to adults at least 18 years of age for the prevention and treatment of oral mucositis.

Subjects will enter the Screening Period once the informed consent process has been completed. Subjects who are scheduled to receive radiation with or without concurrent chemotherapy and meet all of the inclusion criteria and none of the exclusion criteria will be eligible for the study:

Once subject eligibility is confirmed the subject will start SAN005 treatment on Day 1 of their radiation treatment. All subjects will receive active medication in the study with the first dose administered on Day 1.

Subjects will be instructed on the administration of study medication thrice daily till oral mucositis resolves. Subjects will return to the clinic once a week while receiving radiation and then once every two weeks once their radiation has been completed and then until their mucositis has resolved for the Final Study Visit.

Preliminary Efficacy Evaluation will be the severity of pain rated by the NRPS and mucositis grade by RTOG criteria at Visit 7 (Day 36). Additional secondary efficacy evaluations will include the severity of pain rated by the NRPS and mucositis grade by RTOG criteria at each study visit, frequency of the PEG tube for feeding during the duration of treatment and weight loss from baseline through Visit 5 and 7. The time of mucositis onset and duration will also be used in assessing efficacy. Additional secondary and exploratory endpoints will be outlined in the statistical analysis plan. The overall efficacy is determined by comparing the data to historical controls.

Safety will be assessed by evaluating adverse events (AEs) with respect to severity, duration, and relationship to study drug. In addition tolerability evaluations will be performed at each study visit.

During the active treatment period, subjects will return to the study site according to the study schedule for interim assessments, review of subject dosing diaries, and assessment of concomitant medication and adverse events (AEs).

The study design is summarized in Figure 3-1.

Figure 3-1 **Study Design**

Pretreatment	Treatment		Follow-up
Day 0	Day 1 Baseline	Day 8,15,22,29,36,43 (\pm 2 day, weekly)	Every other week until mucositis resolves or it reaches Visit 10

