6.0 VISIT SCHEDULE AND ASSESSMENTS

6.1 Study Procedures

The visit schedule and assessments are summarized in Table 5-1. A patient will have a maximum of 10 visits: a pretreatment Visit (Visit 1), weekly treatment visits (Visit 2 – 8), and if the mucositis persists, follow-up visits (Visit 9 -10) every other week until the patient's mucositis has resolved which is estimated out to be approximately 9 to 11 weeks after Day 1 treatment initiation.

Source documents will be completed at each patient's visit, and the data captured in the source documents will be subsequently entered into the case report forms (CRFs) by the Investigator or designee.

Table 6–1 Time and Events

Footnotes to Table 1: Time and Events

- ^a Site staff will follow the requirements of the local IRB if required to obtain informed consent from the subjects.
- ^b Only pertinent medical history will be recorded for each subject including smoking history and alcohol intake.
- ^c A serum pregnancy test will be completed for all women of child-bearing potential before radiotherapy simulation.
- ^d Adverse events will be collected after the subject's first treatment and throughout the trial.

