6.4 Withdrawals

The following medical and other reasons justify a premature termination (by subject or investigator) of any of the study products:

- Adverse event (including any SAE, clinically significant AE, intercurrent illness, or other medical condition that indicates to the investigator that continued participation is not in the best interest of the subject);
- Death;
- Lost to follow-up;
- Noncompliance with study medication dosing regimen, protocol requirements, or study-related procedures;
- Investigator discretion in case of occurrence of any medication condition, requirement for prohibited concomitant medication or treatment, or circumstances that would not allow the subject to adhere to protocol requirements;
- Pregnancy;
- Study terminated by Sponsor;
- Withdrawal of consent;

If a subject withdraws from the study, all efforts will be made to complete a final evaluation, if possible. Subjects discontinued due to an AE will be followed until the AE is resolved, a reasonable explanation is provided for the event, or the subject is referred to his/her own primary medical doctor. The specific AE in question will be recorded on the appropriate CRF. All subjects who are withdrawn should complete return to the clinic for a final assessment.

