7 STUDY TREATMENT

7.1 Formulation

The product ingredients are consistent with other retail and OTC products at acceptable concentrations.

Formulation information is presented below in Table 7-1.1

Table 7-1. Santalis Mouth Rinse

Active ingredient	0.5% EISO
Inactive ingredients	Polysorbate-80 NF, Poloxamer 407 NF, Xylitol NF, Sorbitol 70% Solution USP, Menthol USP, Peppermint Oil NF, Sodium Saccharin USP, Purified Water USP
Dosing schedule	30 mL to be used thrice daily for approximately 10 weeks or until mucositis resolves.
Manufacturer	Pam Lewis and Associates, Boerne TX
Packaging	1 Liter bottles
Storage requirements	Store at controlled room temperature ^a (20°C to 25°C [68°F to 77°F])

a: Controlled room temperature indicates a temperature maintained thermostatically that encompasses the usual and customary working environment of 20°C to 25°C (68°F to 77°F). Excursions are allowed between 15°C and 30°C (59°F and 86°F).

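### No contact tied to the last dose appears in the readable protocol, so 0 to 28 days of the 4-week SAE window rely on passive reporting, depending on which stated dosing end applies

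*Combined protocol and SAP*

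**What the plan says.** **Reporting window.** Section 7.8.1.3 says that any SAE arising after consent and "until 4 weeks after stopping study drug treatment must be reported". A separate sentence on deaths covers a death during the study, or one "which comes to the attention of the investigator within 4 weeks after stopping treatment, must be reported".

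**Scheduled contact.** The synopsis (Follow-up Period, Visits 9 to 10) provides clinic visits every second week after radiotherapy "until either mucositis resolves or it reaches Visit 10, whichever is earlier". Section 6.1 limits a subject to 10 visits. Visits 9 and 10 both include a query for adverse events (synopsis and Section 6.2.3).

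**End of dosing.** Three statements differ:
- Synopsis, Trial Design: "Subjects will be instructed on the administration of study medication thrice daily throughout the duration of radiation therapy".
- Section 3.1: "thrice daily till oral mucositis resolves".
- Table 7-1 in Section 7.1: "30 mL to be used thrice daily for approximately 10 weeks or until mucositis resolves".

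**Other safety follow-up.** Footnote d to Table 6-1 has adverse events collected from the "first treatment and throughout the trial". Section 6.4 says "Subjects discontinued due to an AE will be followed until the AE is resolved", or is explained, or the subject is referred to their own doctor; other withdrawn subjects are asked back for one final assessment. Section 7.8.1.2 says in general terms that recorded AEs are followed up where appropriate, with end date and outcome noted.

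**The concern.** The reporting duty runs from the last dose, whereas scheduled contact runs from the end of radiotherapy and stops on an efficacy outcome, resolution of mucositis. Nothing in the readable text brings the two together. Section 7.8.1.3 gives the site 24 hours to inform the sponsor once it learns of an SAE, but after the last visit no planned step makes the site learn of one.

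Safety is one of the three objectives in Section 2, and Section 8.5.5 bases its assessment on the frequency and severity of AEs. With up to 15 treated subjects, one subject whose only SAE goes unrecorded changes the proportion with an SAE by 1/15, or 6.7 percentage points. If part of the window is unobserved, finding no late SAEs says little about whether any occurred.

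**Working it through.** The protocol gives no figure for coverage of the window, so there is none to reproduce. The check is calendar arithmetic.

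**Inputs**
- Window: 4 weeks × 7 = 28 days after the last dose (Section 7.8.1.3).
- Visit 8: Day 43 (Figure 3-1).
- Visits 9 and 10: 2 and 4 weeks after radiotherapy ends (every second week, synopsis and Section 6.2.3), each ±2 days.
- Last day of radiotherapy, R: not stated. Assumed to be Day 43, 46 or 50.

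**Visit timing.** Visit 9 = R + 14 and Visit 10 = R + 28; weeks after Day 1 = (day − 1)/7.
- R = 43: Days 57 and 71, or 8.0 and 10.0 weeks.
- R = 46: Days 60 and 74, or 8.4 and 10.4 weeks.
- R = 50: Days 64 and 78, or 9.0 and 11.0 weeks. This matches the 9 to 11 weeks in Section 6.1.

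**Formula.** With D the day of the last dose and L the day of the last scheduled contact, uncovered days = (D + 28) − L.

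| Dosing end | Last contact | Calculation | Uncovered days |
|---|---|---|---|
| End of radiation (synopsis), D = R | Visit 10 | (R + 28) − (R + 28) | 0 |
| same | Visit 9 | (R + 28) − (R + 14) | 14 |
| same | End of radiation, mucositis already resolved | (R + 28) − R | 28 |
| Resolution (Section 3.1), D = L | Visit at which resolution is recorded | (L + 28) − L | 28 |
| About 10 weeks (Table 7-1), D = 71 | Visit 10, R = 43 | 99 − 71 | 28 |
| same | Visit 10, R = 46 | 99 − 74 | 25 |
| same | Visit 10, R = 50 | 99 − 78 | 21 |

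All results carry the ±2-day visit window. In the first four rows R or L cancels, so the assumed length of radiotherapy does not matter; it matters only for the 10-week reading. If mucositis resolves before 10 weeks, the Table 7-1 wording gives the same 28 days as Section 3.1.

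**Scale, with assumed rates only.** The documents give no SAE rate. If a proportion p of 15 subjects had an SAE in a fully uncovered window, the chance of at least one such subject is 1 − (1 − p)^15:
- p = 2%: 26%
- p = 5%: 54%
- p = 10%: 79%
- p = 20%: 96%

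These are chances that an event occurs, not that it goes unreported.

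**With a contact at D + 28.** Setting L = D + 28 gives 0 uncovered days in every row.

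**The case against.** The strongest reply is that the duty to report does not depend on the visit schedule. Section 7.8.1.3 obliges the site to report any SAE in the window, and Section 7.8.1.2 takes AEs volunteered by the subject or found by other means. If dosing stops with radiation, Visits 9 and 10 query adverse events at about 2 and 4 weeks, and a subject who reaches Visit 10 is fully covered. The study has at most 15 subjects, is not powered, and summarises AEs descriptively. The body of Table 6-1 is not in the readable text, so a telephone contact listed only there cannot be excluded.

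Most of this stands, and it rules out several stronger readings that a reader might infer:
- *No contact covers any of the window.* Not so under the synopsis dosing end.
- *Late events would be missed.* They could be; the reporting duty remains, but finding the events becomes passive.
- *Subjects whose mucositis resolves early are systematically observed less.* That holds only if dosing stops with radiation. Under Section 3.1 about 28 days are uncovered whenever resolution occurs.
- *A completer with an ongoing AE has no follow-up at all.* Section 7.8.1.2 states follow-up in general terms, though it sets no contact or time.
- *The death sentence opens a gap.* It turns on when the investigator hears of the death, while the SAE rule turns on when the event occurs. Death is itself an SAE outcome, so a death within the 4 weeks is reportable anyway. The difference is one of wording.

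The reply does not show any planned means of learning about events after the last visit. The 10-visit cap in Section 6.1 also argues against an additional visit in the unseen table.

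**Conclusion.** The point holds in a limited form. The 4-week window is explicit, and no readable text ties a contact to the last dose. Between 0 and 28 days of the window (±2 days) fall after the last scheduled contact: about 28 under Section 3.1, about 21 to 28 for dosing to about 10 weeks under Table 7-1, and 0, 14 or 28 under the synopsis. SAEs and deaths in that part could be under-counted.

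It is tempting to conclude that the safety result would look too favourable. Under-counting can only lower the SAE frequency, but the documents give neither an event rate nor a rate of unreported events, and Section 8.5.5 defines no analysis window, so the size of any bias cannot be derived.

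The figures assume that Visits 9 and 10 fall 2 and 4 weeks after radiotherapy, that dosing to resolution stops at the visit where resolution is recorded (stopping between visits would shorten the gap), and, for the 10-week reading, that radiotherapy ends between Day 43 and Day 50. Confidence is limited by the missing body of Table 6-1.

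**What to change.** 1. Add one telephone contact or chart check by the existing study coordinator about 28 days after each subject's last dose, whatever the reason for stopping. It should ask about death, SAEs and the outcome of any AE ongoing at the last visit. Place it in the synopsis, Sections 6.2.3 and 6.5, and Table 6-1 if it is not already there. Section 6.5 needs editing in any case, because it refers to a Section 6.2.9 that does not exist.
2. Extend footnote d to Table 6-1 so that AE collection covers this contact.
3. Reconcile the synopsis, Section 3.1 and Table 7-1 on when dosing stops, so that the window has a defined start. Which statement applies is for the sponsor and investigator to settle; a contact tied to the last dose works under any of them.
4. Optionally, align the death sentence with the SAE rule by using date of occurrence.

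The cost is protocol wording, at most 15 calls or chart checks, possibly a few more events to report, and a slightly later last-subject-out date.
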